### **5.3 Dose Modification:**

XL 888 and pembrolizumab have class-specific safety profiles based on their mechanism of action but may also cause AEs that overlap. For management of AEs which can be clearly attributed to XL 888 or pembrolizumab, independent dose modification for either agent is allowed. For AEs without clear attribution to either study treatment, management of toxicity should include dose modifications of both agents.

#### **5.3.1 Pembrolizumab**

Adverse events (both non-serious and serious) associated with pembrolizumab exposure may represent an immunologic etiology. These adverse events may occur shortly after the first dose or several months after the last dose of treatment. Pembrolizumab must be withheld for drug-related toxicities and severe or life-threatening AEs as per 3 below. See Section 5.6 for supportive care guidelines, including use of corticosteroids.

Toxicities unrelated to pembrolizumab will not ordinarily result in the modification of pembrolizumab dose. AEs will be defined based on the National Cancer Institute (NCI) Common Terminology Criteria for Adverse Events (CTCAE) version 4.

Table 3 Dose Modification Guidelines for Drug-Related Adverse Events

General instructions:				

 
1. Corticosteroid taper should be initiated upon AE improving to Grade 1 or less and continue to taper over at least 4 weeks.
 
2. For situations where pembrolizumab has been withheld, pembrolizumab can be resumed after AE has been reduced to Grade 1 or 0 and corticosteroid has been tapered. Pembrolizumab should be permanently discontinued if AE does not resolve within 12 weeks of last dose or corticosteroids cannot be reduced to <math>\leq 10</math> mg prednisone or equivalent per day within 12 weeks.
 
3. For severe and life-threatening irAEs, IV corticosteroid should be initiated first followed by oral steroid. Other immunosuppressive treatment should be initiated if irAEs cannot be controlled by corticosteroids.
 
				
Immune-related AEs	Toxicity grade or conditions (CTCAEv4.0)	Action taken to pembrolizumab	irAE management with corticosteroid and/or other therapies	Monitor and follow-up
Pneumonitis	Grade 2	Withhold	
 
• Administer corticosteroids (initial dose of 1-2 mg/kg prednisone or equivalent) followed by taper
 
	
 
• Monitor participants for signs and symptoms of pneumonitis
 
• Evaluate participants with suspected pneumonitis with radiographic imaging and initiate corticosteroid treatment
 
• Add prophylactic antibiotics for opportunistic infections
 

	Grade 3 or 4, or recurrent Grade 2	Permanently discontinue		
Diarrhea / Colitis	Grade 2 or 3	Withhold	
 
• Administer corticosteroids (initial dose of 1-2 mg/kg prednisone or equivalent) followed by taper
 
	
 
• Monitor participants for signs and symptoms of enterocolitis (ie, diarrhea, abdominal pain, blood or mucus in stool with or without fever) and of bowel perforation (ie, peritoneal signs and ileus).
 
• Participants with <math>\geq</math> Grade 2 diarrhea suspecting colitis should consider GI consultation and performing endoscopy to rule out colitis.
 
• Participants with diarrhea/colitis should be advised to drink liberal quantities of clear fluids. If sufficient oral fluid intake is not feasible, fluid and electrolytes should be substituted via IV infusion.
 

	Grade 4	Permanently discontinue		

AST / ALT elevation or Increased bilirubin	Grade 2	Withhold	
 
Administer corticosteroids (initial dose of 0.5- 1 mg/kg prednisone or equivalent) followed by taper
 
	
 
Monitor with liver function tests (consider weekly or more frequently until liver enzyme value returned to baseline or is stable)
 

	Grade 3 or 4	Permanently discontinue	
 
Administer corticosteroids (initial dose of 1-2 mg/kg prednisone or equivalent) followed by taper
 
	
Type 1 diabetes mellitus (T1DM) or Hyperglycemia	Newly onset T1DM or Grade 3 or 4 hyperglycemia associated with evidence of $\beta$ -cell failure	Withhold	
 
Initiate insulin replacement therapy for participants with T1DM
 
Administer anti-hyperglycemic in participants with hyperglycemia
 
	
 
Monitor participants for hyperglycemia or other signs and symptoms of diabetes.
 

Hypophysitis	Grade 2	Withhold	
 
Administer corticosteroids and initiate hormonal replacements as clinically indicated.
 
	
 
Monitor for signs and symptoms of hypophysitis (including hypopituitarism and adrenal insufficiency)
 

	Grade 3 or 4	Withhold or permanently discontinue 		
Hyperthyroidism	Grade 2	Continue	
 
Treat with non-selective beta-blockers (eg, propranolol) or thionamides as appropriate
 
	
 
Monitor for signs and symptoms of thyroid disorders.
 

	Grade 3 or 4	Withhold or permanently discontinue 		
Hypothyroidism	Grade 2-4	Continue	
 
Initiate thyroid replacement hormones (eg, levothyroxine or liothyronine) per standard of care
 
	
 
Monitor for signs and symptoms of thyroid disorders.
 

Nephritis and Renal dysfunction	Grade 2	Withhold	
 
Administer corticosteroids (prednisone 1-2 mg/kg or equivalent) followed by taper.
 
	
 
Monitor changes of renal function
 

	Grade 3 or 4	Permanently discontinue		
Myocarditis	Grade 1 or 2	Withhold	
 
Based on severity of AE administer corticosteroids
 
	
 
Ensure adequate evaluation to confirm etiology and/or exclude other causes
 

	Grade 3 or 4	Permanently discontinue		
All other immune-related AEs	Intolerable/ persistent Grade 2	Withhold	

Based on type and severity of AE administer corticosteroids

	

Ensure adequate evaluation to confirm etiology and/or exclude other causes

	Grade 3	Withhold or discontinue based on the type of event. Events that require discontinuation include and not limited to: Guillain-Barre Syndrome, encephalitis		
	Grade 4 or recurrent Grade 3	Permanently discontinue		
1. Withhold or permanently discontinue pembrolizumab is at the discretion of the investigator or treating physician. NOTE: For participants with Grade 3 or 4 immune-related endocrinopathy where withhold of pembrolizumab is required, pembrolizumab may be resumed when AE resolves to $\leq$ Grade 2 and is controlled with hormonal replacement therapy or achieved metabolic control (in case of T1DM).				

Dosing interruptions are permitted in the case of medical / surgical events or logistical reasons not related to study therapy (e.g., elective surgery, unrelated medical events, patient vacation, and/or holidays). Subjects should be placed back on study therapy within 3 weeks of the scheduled interruption, unless otherwise discussed with the Sponsor. The reason for interruption should be documented in the patient's study record.

### 5.3.2 XL888

The following guidelines are provided for the modification of the dose of XL888 in the event of toxicities attributed by the investigator to this study drug. Toxicities unrelated to XL888 will not ordinarily result in the modification of dose. AEs will be defined based on the National Cancer Institute (NCI) Common Terminology Criteria for Adverse Events (CTCAE) version 4.

In general, subjects experiencing **Grade 1 and 2** drug related toxicities should not have the dose of XL888 modified. However, appropriate supportive care should be provided for the management of drug related toxicities. Grade 2 toxicities may require dose or schedule modifications (delaying or omitting individual doses) due to potentially greater clinical significance; however, this should occur after discussion with study PI. .

Dosing of XL888 must be delayed if a subject experiences a **Grade 3 non-hematologic** toxicity. If the toxicity resolves (returned to baseline or decreased to Grade  $\leq 1$ ) within 14 days, dosing of XL888 may be resumed one lower dose level (See section 5.3.2.1). Exceptions to this rule are as follows:

- Grade 3 fatigue: dose modification are left to the PI's discretion;
- Grade 3 nausea, vomiting and diarrhea: dose modification only after optimal prophylactic measures have failed to control the symptoms adequately;

In the case of Grade 4 **non-hematologic** toxicity, **or persistent Grade 3** toxicity despite one dose level reduction, XL888 will be discontinued.

No dose adjustment of XL888 will be performed for anemia.

No dose adjustment for XL888 will be performed for grade 1, 2, or 3 neutropenia or grade 1, 2, or 3(without bleeding) thrombocytopenia.

Dosing of XL888 will be delayed if subjects develop grade 4 neutropenia or grade 3 thrombocytopenia complicated by bleeding or grade 4 thrombocytopenia. If the toxicity resolves (returned to baseline or decreased to Grade  $\leq 1$ ) within 14 days, dosing of XL888 may be resumed one lower dose level (See section 5.3.2.1).

Dose escalation back to the starting dose will not be allowed.

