**Dose level 3 will only be tested if we observe 2 DLT's on dose level 2.**

### 5.2.2 Dose Escalation

Starting dose of 45mg; if  $\geq 2$  patients with DLTs in 3 ( $\geq 2/3$ ) or 6 ( $\geq 2/6$ ) subjects; stop and consider reduced dose of XL888. If not, increase dose to 90 mg and test 3-6 patients. If  $\geq 2$  patients with DLTs in 3 or 6 subjects, reduce dose to 60 mg and try again. If an acceptable dose is identified, treat 16 more patients at the MTD. Prior to dose escalation, we will obtain approval from the Data Safety and Monitoring Committee (DSMC).

**5.2.3 Dose limiting toxicity (DLT)** will be defined as any of the following definitely treatment related adverse events during the first 21 days of therapy:

- Grade IV neutropenia lasting more than 8 days; any neutropenic fever or sepsis;
- Grade III with clinically significant bleeding or any grade IV thrombocytopenia;
- Grade III nausea, vomiting, or diarrhea, lasting  $>72$  hours despite adequate supportive care;
- Other non-hematologic treatment-related toxicity at Grade III or higher
- Grade 4 asymptomatic laboratory abnormalities that last for more than 24 hours or Grade 3 asymptomatic laboratory abnormalities lasting more than 21 days is a DLT.
- Grade IV or higher diarrhea, nausea, vomiting
- In ability to take more than 75% of XL888 due to toxicity.

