## **5.7 Subject Withdrawal/Discontinuation Criteria**

Subjects may withdraw consent at any time for any reason or be dropped from the trial at the discretion of the investigator should any untoward effect occur. In addition, a subject may be withdrawn by the investigator or the Sponsor if enrollment into the trial is inappropriate, the trial plan is violated, or for administrative and/or other safety reasons. Specific details regarding discontinuation or withdrawal are provided in Section 7.1.4 – Other Procedures.

A subject must be discontinued from the trial for any of the following reasons:

- The subject or legal representative (such as a parent or legal guardian) withdraws consent.
- Confirmed radiographic disease progression

*Note:* For unconfirmed radiographic disease progression, please see Section 5.2.2

*Note: A subject may be granted an exception to continue on treatment with confirmed radiographic progression if clinically stable or clinically improved, please see Section 7.1.2.7.1*

- Unacceptable adverse experiences as described in Section 5.2.1.2
- Intercurrent illness that prevents further administration of treatment
- Investigator's decision to withdraw the subject
- The subject has a confirmed positive serum pregnancy test
- Noncompliance with trial treatment or procedure requirements
- The subject is lost to follow-up
- Completed 24 months of uninterrupted treatment with pembrolizumab or 35 administrations of study medication, whichever is later.

*Note: 24 months of study medication is calculated from the date of first dose. Subjects who stop pembrolizumab/XL888 after 24 months may be eligible for up to one year of additional study treatment if they progress after stopping study treatment provided they meet the requirements detailed in Section 7.1.5.5*

- Administrative reasons

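### Neutropenic fever is dose limiting under 5.2.3, but at a Grade 3 count clearly attributed to XL888 the only neutrophil rule in 5.3.2 is no dose adjustment

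*Combined protocol and SAP*

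**What the plan says.** Section 5.2.3 says that a DLT "will be defined as any of the following definitely treatment related adverse events during the first 21 days of therapy". The first item is "Grade IV neutropenia lasting more than 8 days; any neutropenic fever or sepsis". The limit of more than 8 days belongs to the Grade 4 count; the fever and sepsis limb has no count grade and no minimum duration.

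Section 5.3.2 governs XL888 dosing throughout treatment. For low counts it says "No dose adjustment for XL888 will be performed for grade 1, 2, or 3 neutropenia or grade 1, 2, or 3(without bleeding) thrombocytopenia". It then says "Dosing of XL888 will be delayed if subjects develop grade 4 neutropenia or grade 3 thrombocytopenia complicated by bleeding or grade 4 thrombocytopenia", with resumption one dose level lower if the toxicity resolves within 14 days. Fever and sepsis appear in neither sentence. The XL888-specific toxicities in 5.3.2.2 are visual, hepatic, gastrointestinal and QTc events.

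Three other provisions bear on the point:

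- 5.3.2 has a mandatory rule, "Dosing of XL888 must be delayed if a subject experiences a" Grade 3 non-hematologic toxicity, and stops XL888 for Grade 4 non-hematologic toxicity.
- 5.3 says "For management of AEs which can be clearly attributed to XL 888 or pembrolizumab, independent dose modification for either agent is allowed". Its next sentence says that where attribution is unclear, management should include modifying both agents.
- 5.7 opens its list with "A subject must be discontinued from the trial for any of the following reasons". The nearest triggers are intercurrent illness that prevents treatment, the investigator's decision, and unacceptable adverse experiences described in a Section 5.2.1.2 that does not appear in the protocol.

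**The concern.** The protocol calls neutropenic fever dose limiting when it judges a dose level. When it tells the investigator what to do for the patient who has the event, the one sentence that addresses a Grade 3 neutrophil count points towards giving the next dose unchanged. The platelet rule beside it shows that the authors meant a clinical complication to override a Grade 3 count. Nothing in the text explains why neutrophils are treated differently.

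What is at stake is the safety of an individual patient: re-exposure to XL888 during an episode of neutropenic fever that has been attributed to it. The authority to hold exists. What is missing is a required action.

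**Working it through.** **Step 1. Match each hematologic DLT in 5.2.3 to its XL888 action in 5.3.2.**

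| DLT | XL888 action |
|---|---|
| Grade 4 neutropenia beyond 8 days | Delay (any Grade 4 neutropenia) |
| Grade 3 thrombocytopenia with bleeding | Delay |
| Grade 4 thrombocytopenia | Delay |
| Neutropenic fever, Grade 4 count | Delay, because of the count |
| Neutropenic fever, Grade 3 count | No adjustment is the only neutrophil rule |

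Only the last row is unmatched.

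**Step 2. See whether another provision closes that row.**

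- Unclear attribution: the second sentence of 5.3 directs modification of both agents. Covered.
- Clear attribution to XL888: the first sentence of 5.3 permits modification but does not require it. Not closed.
- Sepsis of Grade 3 or 4: most naturally a non-hematologic toxicity, so delay or discontinuation applies. Covered on that reading.
- Neutropenic fever as such: the documents adopt CTCAE version 4 for grading but do not say whether this event is hematologic. 5.2.3 lists it in the neutropenia item, apart from its item on other non-hematologic toxicity. Not clearly closed.
- 5.7: its nearest triggers need judgement or point to the absent section. Not closed.

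**Step 3. Timing.** Section 7.1.4 puts XL888 on Days 1, 4, 8, 11, 15 and 18 of a 21-day cycle. Assume onset after any dose due that day, with cycles running back to back. Over one week of onset days (Day 1 to Day 7) the waits to the next dose are 3, 2, 1, 4, 3, 2 and 1 days. The range is 1 to 4 days and the mean is 16/7 = 2.3 days. Any 14 consecutive days hold two full weeks, so 2 × 2 = 4 doses fall in the 14-day resolution window. With no adjustment all 4 stay scheduled; under the Grade 4 rule they are held until recovery.

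**Step 4. Frequency.** No rate is stated. The visible background text (4.1.2) gives only ceilings:

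- XL888-IST1 (with vemurafenib, 21 subjects): the serious event terms seen in two or more subjects are named and do not include neutropenic fever. It was therefore a serious event in at most 1/21 = 4.8% (exact 95% upper limit 23.8%), possibly in none.
- XL888-001 (33 subjects): neutropenia is not among events in at least 10% of subjects. Since 10% of 33 is 3.3, at most 3/33 = 9.1% had it at any grade.

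Neither is an estimate for this combination. The event at issue (febrile, Grade 3 count, clearly attributed to XL888) is a subset.

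**The case against.** The strongest reply is that the quoted sentence sets rules by count grade and does not tell anyone to dose through a febrile illness. Section 5.3.2 describes itself as guidelines, 5.3 allows XL888 to be modified, and 5.7 allows a subject to be dropped for any untoward effect. That stands, and a reader should not infer that XL888 must be given during neutropenic fever. A permission is still weaker than the mandatory delay that the same section writes for bleeding, and the stated default points the other way.

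A second reply is that neutropenic fever may count as non-hematologic under CTCAE version 4, so the mandatory Grade 3 delay would already apply. The documents do not settle this. If it does, the change only makes the rule explicit.

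A third is that nothing suggests that XL888 often suppresses neutrophils. Myelosuppression is not among the XL888-specific toxicities, and 5.3.2.2 reports raised neutrophil counts in rats and dogs. This supports reading the event as probably uncommon. It limits the size of the point without removing the mismatch.

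A reader might also infer that sepsis has no XL888 action at all. The text does not support that, because sepsis of Grade 3 or 4 reads most naturally as non-hematologic toxicity with an action already assigned.

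**Conclusion.** The point holds as a narrow patient-safety correction. For neutropenic fever at a Grade 3 count, clearly attributed to XL888, 5.3.2 requires no hold, and its only neutrophil rule is no adjustment. The next dose is then due in 1 to 4 days, and 4 doses stay scheduled over 14 days unless the investigator chooses to hold them.

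This assumes that neutropenic fever is not handled as a non-hematologic toxicity, and that 5.3.2 is read as written. The 4-dose figure counts scheduled doses, not harm. The documents give no event rate.

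It might be inferred that the mismatch distorts dose finding. It does not: 5.2.3 counts a definitely related event in the first 21 days as a DLT whatever is done with later doses, so DLT counting and RP2D selection are unaffected.

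A separate, minor matter is that 45 mg is both the starting dose (5.2.2) and the lowest row of 5.3.2.1. Resuming one level lower therefore has no meaning for the 3 to 6 patients of that cohort. Since 5.3.2 says only that dosing may be resumed, not resuming is the natural reading, but it is not written down.

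**What to change.** In 5.3.2, change the neutrophil limb of the no-adjustment sentence to *grade 1, 2, or 3 (without fever or infection) neutropenia*. Add *neutropenic fever or sepsis* to the events for which XL888 is delayed and may be resumed one dose level lower; sepsis is named for clarity. Keep the delay for any Grade 4 neutropenia, and leave Grade 4 non-hematologic toxicity under its discontinuation rule.

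Optionally, state under 5.3.2.1 that a patient at 45 mg, who has no lower level, discontinues XL888. A 30 mg step could be made from two 15 mg capsules (9.2.1), but the visible text gives no dose data to support it.

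The cost is two short clauses and at most one further line, with no added visits, data or patients. Affected patients will have slightly lower XL888 dose intensity.

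One interaction needs care. 5.2.3 also counts "In ability to take more than 75% of XL888 due to toxicity" as a DLT. Cycle 1 has 6 doses, so skipping two leaves 4/6 = 66.7%, below the threshold. The fever clause adds no DLT where the fever is definitely related and within 21 days, because it already is one. The Grade 4 delay can already raise this question. The optional 45 mg line could add to it: a Grade 4 neutropenia of 8 days or less is not a DLT by itself, but a permanent stop before the Day 15 dose could make it one. If the line is adopted, say how such a stop is counted.

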#### 5.3.2.1 Dose reduction

	Dose	Tablet	Frequency
--	------	--------	-----------

Dose level 1	90 mg	2 capsule (45 mg)	Twice weekly (D 1 and 4)
Dose level -1	60 mg	1 capsule (45 mg) 1 capsule (15 mg)	Twice weekly (D 1 and 4)
Dose level -2	45 mg	1 capsule (45 mg)	Twice weekly (d 1 and 4)

### 5.3.2.2 XL888 Specific Toxicities

#### **A. Visual disturbances**

A variety of visual disturbances have been reported in clinical studies of other HSP90 inhibitors including the following descriptive terms: blurred vision, visual impairment, night blindness, photopsia, flashing, delayed dark/light accommodation, dry eyes, keratitis, conjunctivitis, and ocular surface disease . In a retinal toxicity study of HSP90 inhibitors in beagle dogs, described findings of loss of pupillary light reflex and abnormal wave forms on electroretinography. Histopathologic changes in the photoreceptor cell layer and outer nuclear layer of the retina were described.

Visual disturbances have been reported in subjects on XL888-001 and XL888IST1. On XL888-001, grade 1 – 2 blurred vision was the most common visual disorder reported (5 of 33 subjects (15.2%) with 2 subjects experiencing visual impairment (one Grade 2, one Grade 3/SAE). One subject on XL888-001 was reported to have Grade 2 iritis.

**All patients will have baseline ophthalmologic exam. Repeat ophthalmologic exam will be performed in patients with symptoms. Low grade toxicity (grade 1 or 2) will be managed symptomatically without drug interruption. Grade 3 or persistent grade 2 will require holding the dose and if treatment resumed should be at lower dose level.**

#### **B. Hepatotoxicity**

Liver Function Test Abnormalities Transaminase elevations have been reported in study XL888-001. Four subjects (12.1%) experienced AEs of AST increased (all Grade 3) and two subjects (6.1%) with ALT increased (both Grade 2). Bilirubin elevation (one Grade 3, one Grade 2) were also seen. Increases in ALP, ALT, AST, SDH, and GGT present in both rat and dog preclinical studies following XL888 administration, consistent with potential hepatotoxicity of this agent. Subjects on XL888 should have liver function tests at baseline and at regular intervals while on treatment.

XL888 will be interrupted for rising transaminases as follows:

1. Transaminase increase to  $> 5 \times \text{ULN}$  [upper limit of normal] in subjects with levels less than  $2.5 \times \text{ULN}$  at baseline
2. Doubling of transaminase level for those subjects with elevated baseline transaminases (levels equal or greater than  $2.5 \times \text{ULN}$ )
3. Isolated elevations of total bilirubin ( $>2\text{XULN}$ ) without other explanation.

Subjects with XL888-related transaminase elevations will have weekly monitoring of transaminases. XL888 will be resumed after transaminases return to baseline and patients will have a dose reduction.

XL888 should be discontinued if hepatic dysfunction is not reversed despite interruption of study treatment for 3 weeks.

Elevations  $>3 \times$  ULN of ALT or AST concurrent with  $>2 \times$  ULN total bilirubin without other explanation can indicate drug induced liver injury and drug should be permanently discontinued.

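### The general and hepatic XL888 rules (5.3.2 and 5.3.2.2 B) contradict each other for an isolated Grade 4 transaminase rise and for a Grade 3 rise that recovers on days 15 to 21

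*Combined protocol and SAP*

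**What the plan says.** **General rule, section 5.3.2.** It applies to toxicity that the investigator attributes to XL888. After a Grade 3 non-hematologic event XL888 is held. If the event returns to baseline or Grade 1 or less "within 14 days, dosing of XL888 may be resumed one lower dose level (See section 5.3.2.1"). The paragraph then says "Exceptions to this rule are as follows" and lists two items: Grade 3 fatigue, and Grade 3 nausea, vomiting and diarrhea. After that list comes a stopping sentence, which covers Grade 4 non-hematologic toxicity and a persistent Grade 3 "toxicity despite one dose level reduction, XL888 will be discontinued".

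**Hepatic rule, section 5.3.2.2 B.** XL888 is interrupted when transaminases exceed 5 x ULN (baseline below 2.5 x ULN), when they double from a higher baseline, or when bilirubin alone exceeds 2 x ULN without other explanation. For transaminases: "XL888 will be resumed after transaminases return to baseline and patients will have a dose reduction". There are two stopping conditions. One is time: "XL888 should be discontinued if hepatic dysfunction is not reversed despite interruption of study treatment for 3 weeks". The other is ALT or AST above 3 x ULN together with bilirubin above 2 x ULN and no other explanation.

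**Dose table, section 5.3.2.1.** The rows are 90, 60 and 45 mg, with nothing below 45 mg. Section 5.2.2 opens with "Starting dose of 45mg".

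**The concern.** Both rules apply to the same event in the same patient, and no sentence ranks them. Liver events are expected with this drug. Section 5.3.2.2 B reports of XL888-001: "Four subjects (12.1%) experienced AEs of AST increased (all Grade 3"), and it describes matching liver signals in rats and dogs.

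The first stake is safety. After an isolated Grade 4 transaminase rise, one rule stops XL888 for good and the other re-exposes the patient at a lower dose. Which happens depends on the paragraph the investigator consults.

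The second stake is the toxicity profile, a secondary objective (3.2). The same liver event would be tabulated as an AE leading to discontinuation (8.6.1.1) under one rule and as a dose reduction (8.6.1.3) under the other.

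**Working it through.** The plan gives no figure to reproduce here, so the check sets the two rules side by side. I assume that Grade 3 and Grade 4 rises exceed B's trigger for interruption. The documents adopt CTCAE v4.0 but do not print its cut-offs.

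| Event attributed to XL888 | 5.3.2 | 5.3.2.2 B | Result |
|---|---|---|---|
| Grade 3, at 60 or 90 mg, back to baseline by day 14 | may restart one level lower | resume with a reduction | compatible |
| Grade 3, back to baseline on days 15 to 21 | restart window has closed | resume with a reduction | conflict |
| Grade 4, B's bilirubin criterion not met, back to baseline within 3 weeks | discontinue | resume with a reduction | conflict |
| Grade 4, B's bilirubin criterion met | discontinue | discontinue | agree |
| No recovery by 3 weeks | no restart permitted | discontinue | agree |
| Any restart for a patient already at 45 mg | needs a lower level; none exists | needs a reduction; none defined | gap in both |

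The windows are 14 days against 3 x 7 = 21 days, so they differ by 7 days. That 5.3.2 forbids a restart after day 14 is an inference. It makes permission conditional on 14 days and does not say what follows.

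**How many patients come under both rules.** The inputs are 4 Grade 3 AST increases in 33 patients (5.3.2.2 B) and a planned total of 38 to 50 (8.1).

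- Rate: 4/33 = 0.121. The exact (Clopper-Pearson) 95% CI is 0.034 to 0.282.
- Expected number: 38 x 4/33 = 4.6 and 50 x 4/33 = 6.1.
- Over the interval: 38 x 0.034 = 1.3 to 50 x 0.282 = 14.1.
- Attribution to XL888 is not reported. If only 1 or 2 of the 4 events counted: 38 x 1/33 = 1.2 to 50 x 2/33 = 3.0.

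**How many get different instructions.** This is a smaller group.

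- *Late recovery.* If a share f of the Grade 3 events recovers on days 15 to 21, the number is f x 4.6 to f x 6.1. The documents say nothing about f, so the range runs from none of these patients to all of them.
- *Grade 4.* No Grade 4 transaminase rise is described among the 33 patients. For 0/33 the exact two-sided 95% upper limit is 1 - 0.025^(1/33) = 10.6%. That neither rules such events out nor gives a rate for the combination. Patients who meet the bilirubin criterion or do not recover would also have to be subtracted.

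**The case against.** The best defence is that Grade 4 is already settled. The exceptions in 5.3.2 follow the Grade 3 hold-and-restart rule, and both are Grade 3 events. The stopping sentence comes after them without qualification. Section 5.3.2.2 B sits inside 5.3.2 and speaks of interrupted drug, so it can be read as covering lower grades only. On this reading a reader should not infer that the protocol orders rechallenge after Grade 4. That much stands, because the documents also contain a clear instruction to stop. But the limit to lower grades is not written. B's trigger has no ceiling, and its resumption sentence is not conditional. The opposite reading, that the specific section overrides the general one, is not written either. The defence also leaves the two windows unreconciled.

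A second defence is that 5.3.2 is silent after day 14 and B's 3 weeks fill the silence. That is possible, but the 14-day condition then does nothing for transaminases, and they are not a listed exception.

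A reader might add the 45 mg case as a third conflict. It is not one. Both rules tie a restart to a reduction, and neither defines a dose below 45 mg. The supplied 15 mg capsules (9.2.1) would allow a lower dose to be made up, but the plan names none.

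The effect on the analysis is fairly called small. Section 8.3 is descriptive, AEs leading to discontinuation are listed by subject, and the study team reviews the toxicity logs (10.5).

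**Conclusion.** The point holds for two cases: an isolated Grade 4 rise that returns to baseline within 3 weeks, and a Grade 3 rise that recovers on days 15 to 21. The safety instructions contradict each other there, so the text is wrong as written. The severity is minor. The missing dose below 45 mg is a separate gap shared by both rules.

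A reader might take 4.6 to 6.1 as the number of patients given conflicting instructions. It counts those to whom both rules apply, and most combinations of grade and recovery time are handled compatibly. Even that count is generous as a point estimate. XL888-001 reported events regardless of relationship and pooled doses and formulations, with an MTD of 135 mg against a highest dose of 90 mg here. The contradiction itself does not depend on any of these rates.

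Nor do the documents support an effect on DLT counts or the RP2D. Under 5.2.3 a treatment-related asymptomatic Grade 4 laboratory abnormality lasting more than 24 hours is already a DLT. A hold of more than 14 days inside the 21-day window misses at least 4 of the 6 doses (days 1, 4, 8, 11, 15 and 18). Intake is then at most 2/6 = 33%, below the 75% criterion whichever rule is followed.

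**What to change.** Add a line to the exceptions in 5.3.2 that sends transaminase elevation to 5.3.2.2 B. Replace the resumption sentence in B with one rule:

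> XL888 may be resumed one row lower in 5.3.2.1 if transaminases return to baseline within [one stated window: 3 weeks, or 14 days to match 5.3.2]. XL888 is permanently discontinued for a Grade 4 elevation, for no recovery within that window, for Grade 3 elevation after one reduction, or if the patient is already at 45 mg.

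State the same restart condition for the isolated bilirubin trigger, which has none now. If 14 days is chosen, change the 3-week stopping sentence in B to match. The length of the window, and whether to stop at 45 mg or define a lower level, are clinical choices for the sponsor. What matters is that one answer is written down.

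The cost is one replaced sentence and one or two added lines, with no extra patients, visits or drug supply.
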